### Exclusion Criteria (note that we are no longer excluding Veterans with specific health issues)

- Non-Veterans
- A documented current history of active psychosis or other cognitive issues via ICD-10 codes
- Has participated in  $\geq 4$  MOVE! sessions in the past year
- Pregnancy

- PCP stating that Veteran should not participate
- Self-reported inability to read at a 5th grade level due to literacy level or vision problems

With an expected 20% participation rate (based on pilot data) and a 75% retention rate (based on rates from another VA study and other technology-based interventions), we will need to screen 2,615 Veterans with overweight/obesity to enroll a baseline sample of up to 520 Veterans and end with 392 Veterans completing the study. With a screening rate of approximately 30-35 Veterans per week (6 women, 24 men), we will be able to recruit our target population by the middle of Year 3 (recruitment will start the first quarter of Year 2).

Study Arms/Randomization – Under the direction of the study statistician, the PACT teams will be randomized at the provider level using a random number generator to either the PAL Intervention or Enhanced Usual Care intervention arms.

- *PAL Intervention group:* Participants will arrive and complete consenting materials, a Baseline Survey, and the GEM tool. They will then have a brief break if needed. After the break, they will work collaboratively with the Health Coach using tool-generated materials to modify their goals into SMART goals (specific, measurable, attainable relevant, and timely). The patient will then receive materials containing an individualized report with a summary of their personalized advice, initial goals, and barriers and facilitators to weight loss. They will also receive a packet of MOVE! handouts tailored to their questionnaire responses and schedule 10-12 follow-up health coaching phone calls during the next 12 months of intervention. The Health Coach will also inform the patient of the resources available to them at the VA (e.g. MOVE, TeleMOVE!) that can assist them in achieving their goals.

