We will conduct several statistical analyses to describe Veterans participating in the study. Descriptive statistics, including numerical summaries, frequency tables and graphical displays, will be used to present baseline participant characteristics. Exploratory tests, such as chi-square tests and t-tests, will be used to investigate if baseline characteristics are balanced between two randomized arms. Analysis of missing data due to dropout or incomplete surveys will be investigated by inferring a relationship between baseline characteristics/risk factors and 0-1 indicator that defines whether or not a measurement is observed. This analysis will help to identify factors that are likely to be associated with dropout. Additionally, we will investigate whether the dropout rates are different between two arms. For instance, participants with higher levels of motivation may be more likely to be retained in the study. To deal with these missing, we will incorporate the multiple imputation procedure with the regression analyses to be discussed in the following, along with some sensitivity analysis.

In order to assess the impact of neighborhood-level covariates that may help predict weight loss and behavior change, as well as to better understand and report the environmental context of our study participants, we will determine the Veteran's census tracts and block groups. To do this, we will send a csv file containing the patients' addresses to the VA's geocoding service, Geospatial Service Support Center (GSSC), which uses VA's secured proprietary Enterprise Geographic Information System (GIS) software (<https://www.va.gov/oei/docs/va-spatial-data-strategy.pdf>), via the VA's encrypted email. The data will not include the patient's name or apartment number. GSSC will process the data and return a copy of the spreadsheet with the census tract and block group codes added. Once the data is geocoded, the addresses will be purged from the GSSC's database. All applications of geospatial data will be compliant with the objectives and standards established under the VA Spatial Data Strategy (2022).

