## STATISTICAL AND DATA ANALYSIS

First, all the variables will be summarized (intention-to-treat approach) using mean (with standard deviation) and median (with interquartile range for continuous variables and frequency table for categorical variables) overall and by interventions arms, respectively. Then, Mann-Whitney tests for continuous variables and Fisher's exact tests for categorical variables will be used to check if both providers' and Veterans' baseline characteristics are balanced between the intervention arms.

Specific Aims Analysis (main outcomes will be analyzed using intention-to-treat methodology).

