### 1. Test the impact of the PAL intervention on weight change, clinical, and behavioral outcomes

1a: Veterans in the PAL Intervention arm will lose 2.2 kg and 27% will achieve  $\geq 5\%$  weight loss after 12 months of treatment. There will be 0kg weight change in the Enhanced Usual Care arm, and 12% will achieve  $\geq 5\%$  weight loss.

1b: The PAL Intervention will result in improvements in behavioral outcomes (e.g., increased number of steps, increased fruit/vegetable intake, increased attendance to MOVE!) and clinical outcomes (blood pressure, Low Density Lipoprotein (LDL), Hemoglobin A1C, and waist circumference).

1c: The PAL Intervention will increase attendance to MOVE! and/or other intensive programs.

Method: The primary outcome is mean weight loss at 12 months. Mann-Whitney tests for continuous outcomes (e.g., weight loss) and Fisher's exact tests for categorical outcomes (e.g., whether or not Veterans achieve  $\geq 5\%$  weight loss) will be used to compare the two intervention arms at 12 months, respectively. Unadjusted confidence intervals will be computed to measure the effects of the PAL intervention on the outcomes compared with the Enhanced Usual Care. Repeated measures modeling based on mixed models will be conducted to compare outcome variables between intervention arms, utilizing all of the data at Baseline and at follow-up visits. Such modeling can adjust for baseline characteristics (e.g., diabetes, gender), taking into account: a) the correlation among Veterans within providers, b) the correlation among repeated measures within Veterans. Model-based adjusted confidence intervals will be provided to measure the effects of the intervention on the outcomes as well. Although repeated measures modeling can address missing data automatically, assuming it is missing at random, we will use a multiple imputation procedure to conduct sensitivity analyses under the practical assumption of missing not at random. The sensitivity analyses will be conducted using pattern-mixture models to examine if the statistical findings are robust when considering several scenarios, including the least-favorable scenario where the missing data from the PAL intervention arm were to follow the same pattern as that of the observed data from the Enhanced Usual Care arm.

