### 3. Determine the impact of the PAL Intervention on provider and nurse obesity-related counseling practices and attitudes

3a: Veterans in the PAL intervention arm will receive more frequent and higher quality weight management counseling from PCPs than those in the control arm. The intervention will improve PCP self-efficacy, attitudes, and perceived competency in weight management counseling.

Method: Mann-Whitney tests for continuous provider-level outcomes and Fisher's exact tests for categorical provider-level outcomes will be used to compare the two intervention arms at each survey. Confidence intervals of the effects will be computed as well.

Missing Data Analysis (to adjust for response bias) -- Although the repeated measures modeling can address missing data automatically under the assumption of missing-at-random, we will further analyze the missing data due to loss of follow-up or non-response using two popular missing data tools, inverse-probability-weighting approach and multiple-imputations approach. Both missing data approaches utilize the baseline characteristics to adjust for response bias. In addition, we will use multiple-imputations procedure to conduct sensitivity analyses under the practical assumption of missing not at random. Specifically, the sensitivity analyses will be conducted using pattern-mixture models to examine if statistical findings are robust when considering several scenarios, including the least-favorable scenario where missing data from the intervention arm were to follow the same pattern as that of the observed data from the Enhanced Usual Care arm.

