Sample Size and Power Analysis – We base our sample size on within-person weight change at Baseline and 12 months in each arm. We assume an interclass correlation coefficient (ICC) of 0.05 for Veterans within each PCP and an ICC of 0.01 for PCPs within each PACT team. Assuming that at the end of the study we have 5 teams in each intervention arm and recruit and obtain baseline data for 52 Veterans per PACT team (392 Veterans total at 12 months), we will have sufficient power to detect a 2.2kg (SD=6.0kg) difference in weight between the intervention and non-intervention arms. If we do not have PACT attrition (5 PACT teams per arm), then we will have additional power. This amount of weight loss is consistent with findings from the ASPIRE VA study and a systematic review of technology-assisted weight loss interventions in primary care. We will also have the power to detect our hypothesized difference of 15% of PAL Intervention Veterans achieving 5% weight loss (clinically significant—as little as 5% weight loss can improve cardiovascular risk), 85% assuming 12% of intervention arm Veterans achieve this amount of weight loss. We will be able to detect 2.9cm change in waist circumference.

If we assume the missing rate at 12 months is 15%, then we will have 44 evaluable Veterans per team. We assume an interclass correlation coefficient (ICC) of 0.03-0.04 for Veterans within each PACT team and an ICC of 0.01 for PCPs within each team. If the ICC of Veterans within each PACT team is 0.03, the power is 85% to detect a 2.2kg (SD=6.0kg) difference in weight between the intervention and intervention arms; the power is 87% to detect a 2.9cm (SD=7.7cm) difference in waist circumference. This amount of weight loss and waist circumference change is consistent with findings from the ASPIRE VA study and a systematic review of technology-assisted weight loss interventions in primary care. In addition, the power is 91% to detect our hypothesized difference between 25% Veterans in the intervention arm and 10% of Veterans in the control arm achieving 5% weight loss (clinically significant). If the ICC of Veterans within each PACT is 0.04, the powers are 81%, 83%, and 87% to detect the same effect sizes of weight loss, waist circumference, and proportion of 5% weight loss, respectively.

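### The plan does not say how Veterans without a 12-month weight are counted in the ≥5% weight-loss comparison, and its missing-data methods are not tied to that outcome

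*Combined protocol and SAP*

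**What the plan says.** Hypothesis 1a (Aim 1, Statistical and Data Analysis) has two parts: mean weight change, and the proportion losing at least 5%, put at 27% v 12%. The primary outcome is mean weight loss at 12 months. For the proportion, the Aim 1 Method names "Fisher's exact tests for categorical outcomes (e.g., whether or not Veterans achieve" the 5% threshold, with unadjusted confidence intervals. The lead-in to the Specific Aims Analysis says "main outcomes will be analyzed using intention-to-treat methodology".

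Two missing rates are given. The recruitment paragraph after the Veteran exclusion criteria assumes "a 75% retention rate" and expects to "enroll a baseline sample of up to 520 Veterans and end with 392 Veterans completing the study". The second power paragraph says "If we assume the missing rate at 12 months is 15%, then we will have 44 evaluable Veterans per team".

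Missing data are addressed in several places:
- The Statistics Analysis paragraph and the Aim 1 Method rely on mixed models under missing at random.
- The Data Analysis section joins multiple imputation to the regression analyses.
- The Missing Data Analysis paragraph adds inverse-probability weighting and multiple imputation, saying "Both missing data approaches utilize the baseline characteristics to adjust for response bias".
- The Aim 1 Method and the Missing Data Analysis paragraph add pattern-mixture sensitivity analyses. One scenario lets missing PAL data behave like observed Enhanced Usual Care data.

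None of these passages names the ≥5% outcome as their target or says how an unweighed Veteran enters the Fisher table.

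**The concern.** A 2×2 test needs a yes or no for each Veteran it includes. A Veteran with no 12-month weight can be left out, counted as not achieving 5%, or given an imputed status. Each choice can be defended from some sentence of the plan, and nothing fixes the choice before the data are seen. Intention-to-treat says who should be analysed, but does not supply a status for someone who was not measured.

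The unstated default, testing the observed values, is a completer analysis. The plan itself gives a reason to be wary of that: the Data Analysis section remarks that "participants with higher levels of motivation may be more likely to be retained in the study". If those who stay are also those who lose weight, completer rates run high. If retention differs by arm, the difference can be distorted too.

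The imputation and weighting that might correct this are described by reference to baseline characteristics. The 6-month weight, which every Veteran is scheduled to have and which should predict the 12-month result, is not mentioned. What is at stake is the estimate for the outcome that the plan calls clinically significant and for which it claims power.

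**Working it through.** **Inputs from the documents.** 520 enrolled, 75% retention and 392 completers (recruitment paragraph); 15% missing (second power paragraph); 27% v 12% (Hypothesis 1a); 52 enrolled per team, 5 teams per arm, ICC 0.03 (power paragraphs). Assumed: equal arms of 260, and two-sided alpha 0.05, which the plan does not state.

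**Reproducing the plan's counts.** 2,615 × 0.20 × 0.75 = 392.25, matching 392. So 520 − 392 = 128 Veterans (24.6%) have no 12-month weight. On the alternative rate, 52 × 0.85 = 44.2, matching 44 per team, and 0.15 × 520 = 78 are missing.

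**Effect of the scoring rule**, taking 27% and 12% as completer rates and the same proportion missing in each arm:

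| Rule | 25% missing | 15% missing |
|---|---|---|
| Completers only | 27.0% v 12.0%: 15.0 points | 27.0% v 12.0%: 15.0 points |
| Missing counted as not achieved | 0.75 × 27 = 20.25% v 0.75 × 12 = 9.0%: 11.25 points | 0.85 × 27 = 22.95% v 0.85 × 12 = 10.2%: 12.75 points |
| Missing PAL Veterans at the control rate | 20.25 + 0.25 × 12 = 23.25% v 12.0%: 11.25 points | 22.95 + 0.15 × 12 = 24.75% v 12.0%: 12.75 points |

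The third row is the plan's own least-favorable scenario. In the 25% column, with counts rounded to whole Veterans where needed, Fisher p-values that ignore clustering are about 0.0003, 0.0005 and 0.0013.

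**Unequal dropout (assumed 30% PAL, 20% control), missing counted as not achieved.** 0.70 × 27 − 0.80 × 12 = 18.9 − 9.6 = 9.3 points. Reversed: 0.80 × 27 − 0.70 × 12 = 21.6 − 8.4 = 13.2 points.

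**Power at 25% missing**, 5 teams per arm, ICC 0.03, design effect 1 + (m − 1) × ICC:
- Completers: m = 39.2, design effect 2.146, effective n = 196/2.146 = 91.3 per arm. Power for 27% v 12% is about 73%.
- Missing counted as not achieved: m = 52, design effect 2.53, effective n = 260/2.53 = 102.8 per arm. Power for 20.25% v 9.0% is about 63%, assuming the same ICC for the recoded outcome.

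**Bias of the completer analysis under an assumed dropout model.** Here 27% and 12% are the true rates among all enrolled. In each arm, weight loss at 6 and 12 months is bivariate normal with correlation 0.7. The odds of dropout double for each SD less weight lost at 6 months. None of these inputs comes from the documents. By simulation:

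| Missing, PAL v control | True difference | Completers | Imputed without 6-month weight | Imputed by arm with 6-month weight |
|---|---|---|---|---|
| 25% v 25% | 15 | about 16.4 | about 16.4 | about 15 |
| 35% v 15% | 15 | about 18.9 | about 18.9 | about 15 |

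The completer rates are roughly 30% v 14% in the first row and 32% v 13% in the second. With the imbalance reversed, the completer difference can fall below 15 instead. The model has no baseline predictor of weight change. If baseline variables did predict 6-month loss, imputation from them would remove part of the error.

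**The case against.** The strongest reply is that the plan is far from silent on missing data. Both the Statistics Analysis paragraph and the Aim 1 Method apply mixed models to outcome variables in general, and a binary version is not excluded. Multiple imputation, weighting and pattern-mixture analyses are all planned, and ≥5% status could be derived from any imputed weight. This stands. A reader might infer that the plan ignores missing data for this outcome; the documents do not support that. The gap is that no sentence makes the link or says which result is reported as the ≥5% comparison.

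A reader might also infer that Fisher's test can use only completers. It cannot be put that strongly: once a rule is set, the test can include all 520. Intention-to-treat points towards including them, but gives no rule.

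Nor do the documents show that this choice matters more than other analysis choices for the outcome. Whether clustering is allowed for may matter as much or more for power.

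The outcome is not primary, and under equal dropout neither the direction nor the unclustered significance changes. Both points stand and limit the weight of the concern. The bias figures rest on assumed inputs, and the remark on motivated participants is offered as a possibility to investigate, not a forecast. Finally, chart review is planned, but the plan does not say that a chart weight replaces a missed 12-month measurement.

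**Conclusion.** The concern holds in a limited form. For one half of Hypothesis 1a, the plan states intention-to-treat and a test, but no rule for the 15% to 25% of Veterans expected to lack a 12-month weight. Run on observed data, the test is a completer analysis.

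If 27% and 12% are completer rates and dropout is equal, the choice of rule moves the difference from 15.0 to 11.25 points at 25% missing, or to 12.75 at 15%. The sign is unaffected. Under the assumed dependence of dropout on 6-month weight change, a true 15 points shows as about 16.4 among completers with equal dropout, or 18.9 with 35% v 15% missing. Imputation that leaves out 6-month weight does not correct this in that model; imputation that includes it does.

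The plan does not say whether 27% v 12% describes completers or all enrolled, so it cannot be asserted that the 15-point target is a completer figure. The analysis of mean weight loss, the primary outcome, is not called into question by this point. The change should be made, but the trial's main conclusion does not depend on it.

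**What to change.** In the Aim 1 Method:

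1. Make the ≥5% comparison an analysis of all enrolled Veterans. Multiply impute 12-month weight separately by arm from baseline weight, 6-month weight and provider. Derive ≥5% status in each imputed data set and combine the arm difference, allowing for clustering by provider as the planned mixed model does.
2. Apply the pattern-mixture scenarios already planned to the same indicator. Counting missing as not achieved may be added, but need not replace them.
3. Keep the Fisher test if wanted, labelled as a completer analysis.
4. State whether 27% v 12% refers to completers or to all enrolled, and match the power statement to it.

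The cost is some SAP wording and a little programming, since imputation is already planned. The reported difference and the power may turn out smaller.

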Statistics Analysis: First, all the variables will be summarized using mean with standard deviation and median with interquartile range for continuous variables and frequency table for categorical variables, overall and by randomized arms, respectively. Mann-Whitney tests for continuous variables and Fisher exact tests for categorical variables will be used to check if baseline characteristics are balanced between two arms. Second, Mann-Whitney tests for continuous outcomes and Fisher exact tests for categorical outcomes will be used to compare outcome variables (including intermediate outcomes, behavioral outcomes, and weight outcomes) between two arms at 6 months and 12 months, respectively. Wilcoxon rank tests for continuous outcomes and McNemar tests for binary outcomes will be used to compare them between follow-ups and baseline within each arm. Third, repeated measures modeling based on mixed models will be conducted to compare outcome variables between two arms, utilizing all the data at baseline and three follow-ups. Such modeling can adjust for baseline characteristics, take into account the correlation among repeated measures within subjects, and deal with missing data automatically assuming missing at random. Finally, we will conduct sensitivity analysis based on multiple imputation procedures to examine the impacts of missing data under some missing not at random assumptions.

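### The Aim 1 mixed model names no provider-by-visit effect; fitted as ordinary random intercepts with baseline as an outcome, it ignores clustering of weight change, with about 13–18% false positives at the planning ICCs

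*Combined protocol and SAP*

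**What the plan says.** The Aim 1 Method states: "The primary outcome is mean weight loss at 12 months". It lists a Mann-Whitney test for weight loss first, then a repeated-measures mixed model comparing the arms, "utilizing all of the data at Baseline and at follow-up visits". The model may adjust for baseline characteristics, with diabetes and gender as examples, and takes into account "a) the correlation among Veterans within providers, b) the correlation among repeated measures within Veterans". Model-based adjusted confidence intervals are to come from it.

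The Method does not say whether baseline weight is an outcome row or a covariate, whether the tested effect is arm or arm-by-visit, whether the provider effect may change over visits, or which degrees of freedom apply. No significance level is stated anywhere.

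The earlier Data Analysis section describes a similar model that will "take into account the correlation among repeated measures within subjects", with no provider term. The Sample Size and Power Analysis text says: "We base our sample size on within-person weight change at Baseline and 12 months in each arm". It assumes an ICC of 0.05 for Veterans within a PCP and, in its second paragraph, 0.03 to 0.04 for Veterans within a team. Randomisation is at provider level, with 17 units.

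**The concern.** A provider effect on weight level and a provider effect on weight change are different things. The first says that some providers have heavier patients. The second says that some providers' patients lose more weight than others', whatever the arm. When providers are randomised and the outcome is weight loss, only the second inflates the variance of the arm comparison, and it is the one that the sample size appears to budget for.

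A random intercept for provider captures only the first. An analyst could put baseline and follow-up weights in as repeated outcomes, add an intercept for each listed correlation and test arm-by-visit. That would follow the text faithfully and still produce an interval for the primary outcome that takes no account of provider randomisation.

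This matters because no other weight analysis in the plan fills the gap. The Mann-Whitney test ignores clustering, and so does the model in the Data Analysis section. The pattern-mixture and imputation analyses address missing data. The Aim 1 model is the only weight analysis that mentions providers.

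**Working it through.** **The plan's own figure.** The plan states 85% power at ICC 0.03 and 81% at 0.04 for 2.2 kg (SD 6.0). Power = Φ(2.2/SE − 1.96), with SE = 6.0·√(2/n), n = mk/DE per arm and DE = 1 + (m − 1)·ICC.

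- Stated layout, k = 5 teams per arm and m = 44: DE = 2.29, n = 96.1, SE = 0.866 and power 71.9% at ICC 0.03; 64.5% at 0.04. The stated figures are not reproduced.
- k = 10 clusters per arm and m = 22: DE = 1.63, n = 135.0, SE = 0.730 and power 85.4% at ICC 0.03; 80.9% at 0.04. The stated figures are reproduced with a two-sided 5% level.

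The stated powers therefore allow for clustering and match a two-sided 5% level, which is assumed below.

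**Why the provider term cancels.** Write weight for Veteran *i* of provider *j* at visit *t* as

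Y = (visit mean) + (arm and arm-by-visit terms) + u_j + v_ij + e_ijt.

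The 12-month-minus-baseline difference contains neither u_j nor v_ij; only e_ij,12 − e_ij,0 remains, and the model treats that as independent between Veterans of the same provider. With complete data at two visits, the arm-by-visit test is a t test on individual changes. This was checked by fitting the two-intercept model to simulated data: its z statistic agreed with the t test on change to within 0.0002.

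**Size of the error.** Inputs: 17 providers (Project Methods); 392 Veterans at 12 months and SD 6.0 kg (Sample Size and Power Analysis); ICC of change 0.03 to 0.05 (same section, read as applying to change); equal provider sizes and two-sided 5% (assumed).

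- m = 392/17 = 23.06
- Model SE = 6.0·√(4/392) = 0.61 kg
- True SE = model SE × √DE
- False-positive rate = 2·[1 − Φ(1.96/√DE)]

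| ICC of change | DE = 1 + 22.06·ICC | True SE (kg) | False-positive rate |
|---|---|---|---|
| 0 | 1.00 | 0.61 | 5.0% |
| 0.01 | 1.22 | 0.67 | 7.6% |
| 0.03 | 1.66 | 0.78 | 12.8% |
| 0.04 | 1.88 | 0.83 | 15.3% |
| 0.05 | 2.10 | 0.88 | 17.7% |

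Nominal 95% intervals would cover about 87% at ICC 0.03 and 82% at 0.05.

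**Simulation checks under the null** (17 providers of 23):

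- Arm-by-visit test, 6,000 trials per setting: 12.6%, 15.2% and 18.0% at ICC 0.03, 0.04 and 0.05.
- Full mixed-model fits with provider and Veteran intercepts, 400 at ICC 0.05: 17.3%. Some fits gave convergence warnings, so the main weight rests on the formula and the larger simulation.
- Mann-Whitney on change: 12.3%, 14.6% and 17.2% at the same ICCs.
- Test on provider mean changes with 17 − 2 = 15 df, which is what a provider-by-visit term gives with balanced data: 4.9 to 5.3% at every ICC from 0 to 0.05.
- Baseline as a covariate with a provider intercept on 12-month weight: about 6% (400 fits, z test).

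**The case against.** The strongest reply is that the text does not prescribe the model that fails. It says which correlations are taken into account, not that the provider effect is constant over time. A provider effect varying by visit would fit the wording, and so would baseline weight as a covariate or weight loss itself as the modelled outcome. None of these cancels the provider term; the first two gave about 5% and about 6% above. A reader might infer that the plan fixes baseline as an outcome row and that the inflated rate is a property of the plan as written. The documents do not support that, and this part of the reply stands.

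The figures are also conditional. No alpha is stated. That the ICCs describe change is inferred from the sentence on within-person change. The 0.03 and 0.04 values are given for teams, and only 0.05 is given for PCPs. All of this stands too.

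The reply does not make this mere missing detail. Pooling baseline with the follow-ups and naming two nested correlations most naturally suggests the two-intercept model. Testing the arm main effect instead would avoid the cancellation, but it would average in baseline, when no effect can exist, and so would not estimate 12-month weight loss.

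Two further inferences should be resisted. One is a specific larger error rate with three visits and dropout; that depends on a weight trajectory and visit-level error that the documents do not give. The other is that the gender and diabetes adjustment has no effect. The plan does not say that these enter as main effects only. What can be said is that, with complete data and baseline as an outcome, main effects alone leave the change contrast unaltered.

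**Conclusion.** The concern holds conditionally. The Aim 1 Method permits, and most naturally suggests, a model whose test of 12-month weight change carries no provider clustering. If it is fitted that way, the false-positive rate is about 13% at ICC 0.03 and 18% at the PCP-level ICC of 0.05. At ICC 0.05 the model standard error is 0.61 kg where the true value is 0.88 kg.

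This rests on time-constant intercepts, baseline as an outcome row, an arm-by-visit test, 17 equal providers, 392 completers, the planning ICCs applying to change, and a two-sided 5% level. The range is not a bound. It falls to 7.6% at ICC 0.01 and to the nominal 5% if change does not cluster. On the ten-team layout of the power text the same formula gives 18% (m = 39.2, ICC 0.03) to 27% (m = 44, ICC 0.05). The model should be specified before analysis because the plan has no other weight analysis that respects the randomised unit.

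**What to change.** In the Aim 1 Method, name the 12-month arm contrast as the effect, state the significance level, and choose one of two models:

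1. Model 6- and 12-month weight as outcomes, with baseline weight as a covariate and a provider random effect that may differ by visit.
2. Keep baseline weight as an outcome row and add a provider-by-visit random effect. If gender and diabetes are adjusted for, enter them by visit.

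Under either model, use small-sample degrees of freedom such as Kenward-Roger, which will be about 15 with 17 providers. Bring the model description in the Data Analysis section into line so that the two agree.

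The cost is SAP wording only; no design or data-collection change is needed. The downside is wider intervals: at ICC 0.05 the standard error rises from 0.61 to 0.88 kg, and the multiplier from 1.96 to about 2.13 on 15 degrees of freedom.
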